Title: Visual Restoration for Hemianopia

RSRB No.: RSRB00069879

Sponsor-Investigator: [name]. M.B.A.

Principal Investigator (Study Site 1): [name]. M.B.A.
Professor and Chair, Flaum Eye Institute
University of Rochester
[name]
Rochester, NY, 14642
USA

Daytime [contact]

Sub-Investigator 1 (Study Site 2): [name].
Robert Z. & Nancy J. Greene Professor of Ophthalmology
Bascom Palmer Eye Institute
University of Miami Health Services
[name]
Miami, Florida 33136
Daytime [contact]

Sub-investigator 2 (Study Site 3): [name]
Scheie Eye Institute
Department of Ophthalmology
University of Pennsylvania
Philadelphia, PA 19104
Daytime [contact]

Purpose: This project will collect data to quantify the effect of visual training on visual defects resulting from damage to the primary visual cortex. Subjects will be recruited, undergo baseline visual testing, undergo visual training designed to reduce their visual deficit, and perform post-training visual tests. This research is designed to determine if different visual training treatments are capable of reducing visual defects in a large population of adult subjects with cortical blindness in a double blind clinical trial.

Background and Motivation for the study: When brain damage is incurred in adulthood, through stroke, trauma, or other neurodegenerative conditions, functional deficits result depending on the brain region that was affected. As roughly half of the human cerebral cortex is devoted to visual processing, many people who suffer brain damage experience consequent impairments in vision. When damage affects the primary visual cortex (V1), the visual deficits are severe and are described as cortical blindness (CB), or hemianopia/quadrantanopia, depending on the size of the defect. CB dramatically impacts the lives of those affected, decreasing quality of life (Gall et al., 2008; Gall et al., 2009; Gall et al., 2010). CB subjects often lose the ability to drive (de Jong and Warmink, 2003; Papageorgiou et al., 2007), reducing their independence, while others who continue to drive pose a potential danger to themselves and others (Bowers et al., 2009, 2010; Bowers et al., 2014). Those suffering from CB also have other types of impaired daily functioning (Ramrattan et al., 2001), and reduced independence (Jongbloed, 1986).

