Currently, there is no accepted treatment for cortical blindness. Some spontaneous recovery of vision was reported in a portion of subjects during the first 2-3 months following a stroke (Zhang et al., 2006). However, after this period the visual deficit is believed to become stable and permanent (Horton, 2005; Pollock et al., 2011). As such, in the rare instances when subjects are prescribed rehabilitation, it is essentially limited to substitution (Rossi et al., 1990; Peli, 2000) or compensation therapies (Weinberg et al., 1977; Kerkhoff, 1999, 2000; Spitzyna et al., 2007). In the limited number of subjects who benefit from these therapies, quality of life and daily functioning are improved (Weinberg et al., 1977; Spitzyna et al., 2007). However, neither therapy is able to restore any of the lost vision; instead, they are designed to teach subjects how to make use of what vision they have left more effectively (Lane et al., 2010).

In order to restore lost vision, subjects need to undergo restitution therapy. Multiple research studies have shown visual training to recover particular functions within chronic CB fields (See Melnick et al., 2016 for review). These studies have shown that in addition to improving performance on the trained tasks, such training can also recover untrained aspects of vision, such as those measured by standard, clinical visual perimetry (Cavanaugh and Huxlin, 2017). However, none of these studies were unbiased (i.e., subjects were not randomized and no blinding was used). To fill this important gap in the field, we have designed the present double blind clinical trial to assess whether visual restitution training using visual discrimination tasks presented in the blind field are clinically relevant and obtainable in a larger patient population. The trial will involve recruiting CB patients, measuring their baseline visual performance, randomizing them to one of two treatment groups, training them with one of two types of visual discrimination training therapy and bringing them back for a repeat of all baseline visual measurements. The results of this study will be submitted for publication to scientifically and clinically relevant journals, and they will be submitted to the Food and Drug Administration for approval.

Criteria for subject selection

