1. Number of subjects: 20 subjects will be recruited at each of three study sites, leading to a total of 60 subjects. The subjects will be divided randomly into two training cohorts, with 30 subjects receiving one form of visual discrimination training therapy, while the other 30 will receive another form of visual discrimination training.

2. Gender and age range: Subject gender is intended to have an even distribution. Women and men are both susceptible to the conditions that would qualify participation as study subjects in the proposed research. All subjects who have sustained vision losses as a result of brain damage, that are able to give informed consent and are willing and able to undergo testing and training will be eligible for inclusion in this study, subject to the limitations described in the following paragraph. Since vision losses as a result of brain damage do occur in women, we will aim to recruit equal numbers of men and women in the proposed study.

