Eye examination: A complete medical history, eye history, and eye examination will be performed in order to determine eligibility for the study. A comprehensive, routine dilated eye exam that includes slit lamp examination and retinal optical coherence tomography (OCT), will be performed on each patient by a qualified ophthalmologist or neuro-ophthalmologist at each site to verify ocular health. OCT should have a signal strength of at least 6, otherwise the test should be repeated. If any problems or signs of ongoing, developing or progressing eye disease are observed, this will constitute grounds for exclusion from the study. The eye examination will include Snellen best corrected acuity, intraocular pressure measurement, exophthalmometry, motility, external examination, slit lamp examination, dilated fundus examination and OCT imaging of the retina.

Visual field testing: Certified technicians will perform 24-2 Humphrey visual fields on each subject. Fixation and pupil monitoring will be “on” for each test. The examination will be performed twice with a 30-minute rest period after each test. Examinations need to be done twice at baseline, with the second test used for future analysis, to ensure that patients are proficient in performing the tests at baseline, so that we can rule out practice on the test as a reason for post-training improvements. During Humphrey perimetry, the eye tracker will be engaged at all times. Tests will be repeated if the patient fails to generate acceptable test reliability (in terms of rate of fixation breaks, false positives and false negatives). If repeated perimetry tests fail to yield acceptable reliability measures (as per device specifications), this will constitute grounds for excluding the subject from the study. Our research to date shows that accurate fixation is critical both to generate reliable perimetry results (our primary outcome measure) and to elicit training-induced improvements in the blind field. All excluded subjects will be replaced with a new enrollment.

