- requires inpatient hospitalization or prolongation of existing hospitalization;
- is a congenital anomaly/birth defect; or
- requires medical or surgical intervention to prevent permanent impairment or damage.

At each subject visit the site study staff will assess adverse events by recording all voluntary complaints of the subject and by assessment of clinical and laboratory features. At each study visit, the subject should be questioned directly regarding the occurrence of any adverse experience since his/her last visit.

All adverse events, whether observed by the Investigator, elicited from or volunteered by the subject, should be documented. Each adverse event will include a brief description of the experience, the date of onset, the date of resolution, the duration and type of experience, the

severity, the relationship to investigational product, contributing factors, and any action taken with respect to the study device. All adverse events occurring between the time of consenting and subject completion or withdrawal from the study will be recorded. Follow up will continue until the adverse event is resolved, including those unresolved at the time of subject concluding study participation.

Data analysis and data monitoring: HVF test results will be analyzed using a custom program in Matlab. Changes in HVF over time will be mapped across the visual field and the area of the visual field that increases or decreases in sensitivity by >6dB will be quantified. Subject age, lesion age, visual deficit size, and type of precipitating neurologic event will be analyzed using linear regression and ANOVA to determine if any of these factors are correlated with change; when appropriate, post-hoc analyses will be conducted using Tukey's HSD and a family-wise Type I error rate of 0.05.

Data storage and confidentiality

- a. Data will be stored on a secure, encrypted server hosted on the URMC private network. Only study personnel directly involved in raw data processing and analysis will have access to data files containing protected health information.
- b. A separate key will be created linking the subject identifiers with a unique study ID number to avoid any direct identifiers stored with the collected data.
- c. Data collected will be used for future research studies.

Risks/benefit assessment

- a. Risk Category: Minimal risk

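### The only analysis paragraph pre-specifies no use of the randomised training cohort and no test of change, so the plan as written cannot answer the trial's own question

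*Combined protocol and SAP*

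**What the plan says.** The Purpose section sets the question: to "determine if different visual training treatments are capable of reducing visual defects in a large population of adult subjects with cortical blindness". The Background gives the reason for a new trial, namely that "none of these studies were unbiased (i.e., subjects were not randomized and no blinding was used"). Criteria for subject selection, item 1, supplies the design: "The subjects will be divided randomly into two training cohorts", 30 in each. The Baseline Visit section adds double masking. The Screening Visit text on visual field testing identifies the endpoint in passing: "reliable perimetry results (our primary outcome measure"). It also says that fields are taken twice at baseline, "with the second test used for future analysis".

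The analysis itself is one paragraph, headed Data analysis and data monitoring. On the outcome, it says that "the area of the visual field that increases or decreases in sensitivity by >6dB will be quantified". On inference, it says "Subject age, lesion age, visual deficit size, and type of precipitating neurologic event will be analyzed using linear regression and ANOVA", and gives the aim as "to determine if any of these factors are correlated with change". Tukey's HSD with a family-wise error rate of 0.05 is attached to post-hoc work on those factors. There is no separate SAP section, and the paragraph shows no sign of redaction.

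**The concern.** A randomised trial earns its evidential value through an analysis by randomised group. Here the stated models relate patient characteristics to change, which is an observational analysis of the kind the Background faults in earlier work. The randomised factor is left out.

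Two things are at stake. First, the stated output would be the same had nobody been randomised. Second, because no comparison is fixed, the form of the outcome, the covariates, the analysis set and the treatment of missing final fields could all be chosen after the data are seen. That matters more because the Background says the results will go to the Food and Drug Administration.

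**Working it through.** **1. The plan's own figure.** 3 sites × 20 = 60, and 2 cohorts × 30 = 60. The sample size is consistent as arithmetic. The documents give no power, effect size, SD or dropout rate, so it cannot be derived from a test.

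**2. Where the training assignment appears.** It appears in the Background (design), in Criteria for subject selection item 1 (30:30 split), in the Baseline Visit randomisation text (masking, pre-assigned cohort) and under Re-Entry Visits (original schedule kept). All of these concern allocation or conduct. None is an analysis.

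**3. The analysis paragraph, step by step.**
- Mapping and quantifying field change is descriptive. No null hypothesis, test or split by cohort is given.
- Regression and ANOVA are confined by their purpose clause to four factors: subject age, lesion age, deficit size and event type.
- Tukey's HSD follows up those same factors. It is not a disguised cohort comparison, and a two-level cohort factor would not need one.

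**4. Questions set against analyses.**

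| Question the trial could be asking | Analysis needed | Stated? |
|---|---|---|
| Do the two trainings differ? | Between-cohort contrast | No |
| Does each training reduce the deficit? | Within-cohort test of change | No |
| Does training in general reduce it? | Pooled test of change | No |
| Do patient factors relate to change? | Regression/ANOVA | Yes |

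**5. What a cohort contrast can and cannot show.** Let the true mean changes be μ1 and μ2. The contrast estimates μ1 − μ2. It is zero when μ1 = μ2 = 0 and equally when μ1 = μ2 > 0. With two active arms, a null difference cannot tell whether both trainings work or neither does. A within-cohort test addresses μ1 or μ2 directly, but does not use the randomisation. The objective therefore decides which analyses are needed.

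**6. Context on precision (assumed two-sided alpha 0.05; results in SD units because no SD is given).**
- Normal approximation, 80% power: (1.960 + 0.842) × √(2/30) = 2.802 × 0.2582 = 0.72 SD. The noncentral t gives 0.74 SD.
- 95% CI half-width: t(0.975, 58) × √(2/30) = 2.002 × 0.2582 = 0.52 SD.
- If 10% or 20% had no usable final field (assumed; 27 v 27 or 24 v 24), the detectable difference is 0.78 or 0.83 SD and the half-width 0.55 or 0.58 SD.
- Within one cohort of 30, before any multiplicity adjustment: 2.802 × √(1/30) = 0.51 SD of change (t-based 0.53).

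The finding does not depend on these figures.

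**The case against.** The strongest reply is that a cohort comparison is implied by randomising two groups, and that the Purpose may concern improvement under training and not superiority of one training over the other. Both points are fair, and neither closes the gap. An implied comparison fixes no outcome, model, alpha or analysis set. If improvement is the aim, no test of change is stated for that either. What does stand is that the objective must be settled first: no section states a superiority hypothesis, so it would be wrong to assume that within-cohort change is merely supportive.

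Several stronger readings are tempting, and the documents do not support them:
- A reader might infer that the sponsor will not compare the cohorts. The text is silent, which shows only a lack of pre-specification.
- A reader might infer that masking is wasted. It still protects subject effort and test conduct whatever model is fitted.
- A reader might infer that re-entry subjects have no assignment rule. Re-Entry Visits keeps their original randomisation schedule; only the baseline to be used is open.
- A reader might infer that randomised subjects with unreliable fields can be replaced. That rule sits under the Screening Visit, and the recruitment section ties replacement to screening failure.
- A reader might infer from 0.74 SD that the trial is underpowered. With no SD or target effect in the documents, that cannot be judged.

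How the eyes are combined and how missing fields are imputed are choices for the sponsor, not errors in the plan.

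**Conclusion.** The concern holds and must be fixed. Followed as written, the plan analyses four patient factors and produces no cohort contrast and no test of change, within cohort or pooled. It therefore gives no estimate, interval or test using the 30:30 randomisation that is the trial's stated reason, and no inferential answer to the question in the Purpose. This is more than missing detail, because the randomised factor is absent from the analysis that is stated. The conclusion rests on reading the whole combined document and needs no numerical assumption. The precision figures are context only.

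**What to change.** Before unmasking:

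1. State the objective: a difference between trainings, improvement within each, or both.
2. Name one subject-level Humphrey outcome, such as the area improving by more than 6 dB or a 24-2 index, and say how the two eyes give one value.
3. Add a linear model of that outcome on randomised cohort, adjusted for baseline deficit size (or the baseline value of the same index). Analyse subjects as randomised and report the adjusted difference with a 95% CI at two-sided alpha 0.05.
4. If the objective is improvement within each cohort, also pre-specify the within-cohort tests with multiplicity control, and state the limit that two active arms place on a null difference.
5. Keep the four-factor analysis as secondary, with cohort in the model.

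Minor clarifications: say that the second-test rule, worded for baseline, also applies at Visit 4, where fields are again taken twice. Say which baseline is used for re-entry subjects. Say whether fields from NOTRAIN visits (where the plan already requires all regular activities) and from withdrawal visits enter the analysis.

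The cost is a short section of analysis wording, using data already collected. The documents do not show whether unmasking is still ahead. If it is not, analyses added now should be reported as not pre-specified.

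### The family-wise 0.05 covers only post-hoc Tukey comparisons, not the search across four patient factors, and the factor models omit the randomised cohort

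*Combined protocol and SAP*

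**What the plan says.** All of the planned inference is in one sentence of Data analysis and data monitoring. It names the factors and methods: "Subject age, lesion age, visual deficit size, and type of precipitating neurologic event will be analyzed using linear regression and ANOVA". It gives the aim as "to determine if any of these factors are correlated with change". It then adds: "when appropriate, post-hoc analyses will be conducted using Tukey's HSD and a family-wise Type I error rate of 0.05".

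The response comes from the sentence before it, under which "the area of the visual field that increases or decreases in sensitivity by >6dB will be quantified". Visual field testing under the Screening Visit calls perimetry the primary outcome measure.

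On design, item 1 of Criteria for subject selection plans 60 subjects at three sites and says "The subjects will be divided randomly into two training cohorts", with 30 in each. Training cohort does not appear among the factors or in any stated model.

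The document gives no significance level for the four factor tests, no adjustment across them, no testing order, no overall test and no exploratory label. No other section deals with multiplicity.

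**The concern.** The word "any" in the stated aim makes this a search, since one positive test out of four is enough to name a predictor. A reader who sees a family-wise rate of 0.05 in the same sentence may take it that the search is protected at that level. As written, the rate belongs to the post-hoc step. The named method could not protect the search in any case, because Tukey's procedure compares group means within one categorical factor. Age, lesion age and deficit size are naturally continuous. Event type has two eligible causes under item 5 of the inclusion criteria (ischemic or hemorrhagic).

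At stake is a claim that some patient characteristic predicts recovery on the primary measure when none does.

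The second matter is efficiency. The factor models are fitted to subjects from two randomised training cohorts. Any difference in mean change between the cohorts stays in the residual and makes a real predictor harder to detect.

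**Working it through.** **Inputs from the protocol.** Four factors, a family-wise 0.05 for post-hoc Tukey comparisons, 60 subjects, 30 per cohort, and two eligible event types.

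**Inputs assumed.** Each factor is tested two-sided at 0.05 in a separate model. The simulations use three normal factors and one binary factor with a 20/80 split. Correlation between factors runs from 0 to 0.7. The cohort difference is 0, 0.5 or 1 SD of change.

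**1. What the stated 0.05 covers.** It is a nominal level, so there is no derived figure to reproduce. For one test, or one Tukey family, the error rate is 0.05 as stated. With two groups and 58 degrees of freedom, the Tukey critical value is q/√2 = 2.0017 and the t critical value is also 2.0017. With the two eligible event types, Tukey is therefore just the t test and controls nothing extra.

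**2. Error across the four factors.** If the tests are independent, the chance of at least one false predictor is 1 − 0.95⁴ = 1 − 0.8145 = 0.185. The upper bound under any dependence is 4 × 0.05 = 0.20. Simulation with n = 60 and no true predictor (20,000 runs per setting; each pair gives no cohort effect / 1-SD effect):

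| Factor correlation | Cohort in model | Cohort omitted |
|---|---|---|
| 0 | 0.192 / 0.187 | 0.192 / 0.186 |
| 0.3 | 0.174 / 0.169 | 0.173 / 0.174 |
| 0.5 | 0.167 / 0.162 | 0.164 / 0.163 |
| 0.7 | 0.144 / 0.141 | 0.143 / 0.142 |

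The range is about 14–19%. The two columns agree within simulation error, so leaving cohort out does not raise the error rate. Holm across the four cohort-adjusted p-values gives 0.041–0.050.

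**3. Power lost by omitting cohort.** With equal allocation, a cohort difference of d SD adds d²/4 to the residual variance: 0.5²/4 = 0.0625 at 0.5 SD and 1²/4 = 0.25 at 1 SD. Unadjusted power for one true factor in simulation:

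| Correlation with change | Cohort effect | Cohort in model | Cohort omitted |
|---|---|---|---|
| 0.4 | none | 0.887–0.892 | 0.893–0.896 |
| 0.3 | none | 0.639–0.652 | 0.648–0.659 |
| 0.4 | 1 SD | about 0.89 | 0.808–0.815 |
| 0.3 | 1 SD | about 0.65 | 0.540–0.555 |

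The cohort term costs at most about 1 point when cohort has no effect. It gains 8–10 points at 1 SD and about 2 points at 0.5 SD.

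**4. Power cost of Holm, cohort in the model.** At correlation 0.4, power falls from 0.887–0.896 to 0.751–0.764. At 0.3 it falls from 0.639–0.653 to 0.431–0.451.

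**The case against.** The strongest reply is that these are patient characteristics, few in number and named in advance, and not the randomised comparison. Nothing in the document lets a predictor result decide efficacy, eligibility or an approval claim. That stands. A reader might infer that a 14–19% false-predictor rate on the primary measure is a 14–19% false-efficacy rate. The document does not support that inference, and the point is minor for this reason.

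A second reply is that the 14–19% depends on one reading. The plan does not say whether the four factors enter separate models or one joint model. A joint regression gated by an overall F test gives 3.8–5.0% under the same null. That also stands as a condition on the figure. But no such gate is stated, so the gap in the text remains.

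A third reply is that an exploratory analysis does not need strict family-wise control, and that Holm is expensive here. This is accepted: the label alone is an adequate remedy, provided it is written down.

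Three further readings are tempting but go beyond the text.
- **Several responses.** The plan leaves open whether area gained or area lost is regressed, so one might suppose that several responses would be tried in turn, inflating error further. Nothing says so, and a net area is not mentioned.
- **One response.** Nor does it follow that one response must be named to control error, since an adjustment could span all the tests.
- **Finer event types.** One might suppose event type has three or more levels, giving Tukey more to do. Only two causes are eligible, and no finer categories are stated.

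**Conclusion.** The concern holds in limited form. The stated family-wise 0.05 protects only comparisons between levels within a categorical factor, and nothing stated protects the search across the four factors. If separate models are each tested at 0.05, which the plan does not say, the chance of at least one false predictor is about 14–19% for factor correlations from 0.7 down to 0.

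Omitting training cohort is a separate matter of efficiency and not of validity. The size of the gain from including it depends on a cohort difference that the document does not give.

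Severity is minor. A reader might infer that adding a cohort term would supply the trial's treatment comparison. It would not: in these models cohort is a covariate, and a between-cohort comparison has to be specified in its own right.

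**What to change.** In Data analysis and data monitoring:

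1. Include training cohort as a term in the model for each factor. Cohort is known for every randomised subject, so no new data are needed. The cost is at most about 1 point of power if the cohorts do not differ.
2. State that the family-wise 0.05 applies only within Tukey comparisons of the levels of a factor.
3. For the search across factors, choose one of two courses and write it down: label it exploratory, or apply Holm at family-wise 0.05 across the four cohort-adjusted p-values.

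The label costs no power but gives no error control. Holm brings the error to 4–5% at the power cost shown in step 4 of the working. The choice is a trade-off for the sponsor. All of this is analysis wording, with no added visits or subjects.
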